To further implicate the role of dysregulated angiogenesis in GI bleeding in CF-LVAD patients, Houston et al. evaluated the use of angiotensin-converting enzyme inhibitor (ACEI) and angiotensin receptor blocker (ARB) therapy in reducing the risk of GI bleeding. Ang-2 expression has previously been shown to be induced through angiotensin II signaling⁹. Houston et al showed that of the patients who did not receive angiotensin II antagonism, 48% experienced GI bleeding. In contrast, only 24% of the patients who received ACEI or ARB experienced GI bleeding¹⁰.

In the most recent J-MACS (Japanese registry for Mechanically Assisted Circulatory Support registry) report, GI bleeding occurred in 4 of 259 patients followed during a 5-year period¹¹. This is in stark contrast to the latest INTERMACS update that reports a rate of 16.24 events of GI bleeding per 100 patient months in the first 3 months after implantation, and 4.08 events per 100 patient months in the 3-12 months after implantation¹². What accounts for this difference? One possibility may lie in the Japanese diet, which is rich in omega 3 fatty acids (O3FA) compared to the diet of patients in the United States. We performed a retrospective study in a cohort of 166 patients with CF-LVAD to assess this theory. Patients who received high-dose O3FA as part of a recovery protocol were compared to those who did not. The frequency of GI bleeding was significantly lower in the O3FA group compared with the control group (0.077 ± 0.419 events/year vs. 0.305 ± 0.847 events/year, $p = 0.033$), leading to a higher 1-year event-free rate in the O3FA group compared to the control group (97% vs. 79%, $p = 0.046$).

In the past decade, there has been an emergence of interest in the human gut microbiota. Using next-generation sequencing (NSG), studies have been able to characterize with great detail the gut microbiome in humans. Further studies have shown that the microbiota is affected by patient characteristics (age, sex, body mass index, lifestyle), diet, and pathologic diseases¹³. In particular, O3FA and its effect on the gut microbiota has been studied, showing that an increase in dietary or supplemental O3FA changes the fingerprint of the microbiome¹⁴⁻¹⁶. O3FA and the microbiome also have a presence in the cancer literature. It is postulated that O3FA play a role in the prevention and treatment of cancer by reduction in cell proliferation, cell survival, angiogenesis, and inflammation¹⁷.

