The data presented thus far shows a possible link between O3FA, GI bleeding, and abnormal angiogenesis, and may be related to the microbiome in CF-LVAD patients. This prospective randomized study aims to evaluate the effect of supplemental O3FA on the frequency of GI bleeding in patients implanted with CF-LVAD both as primary and secondary prevention.

Additionally, we will investigate the effect of O3FA on angiogenesis parameters (Ang-1, Ang-2, VEGF, TNF- α) and the microbiome.

STUDY ENDPOINTS

The primary endpoint will be a change in angiogenesis markers resulting in dysregulated angiogenesis, as described above. Secondary endpoints include rate of GIB and improvement in inflammatory markers.

STUDY INTERVENTION

The study intervention being evaluated is high-dose O3FA (4,000 mg), which is an over-the-counter supplement. Heart failure patients are routinely instructed to take an O3FA supplement for heart health. The research team will fund the supplement, which will be stored in the heart failure office. Once a patient is enrolled, a total of 1 year of supplement will be given to the patient for consumption at home.

PROCEDURES INVOLVED

We will perform an open-label, prospective, randomized control study in which 120 CF-LVAD patients are enrolled. We plan to have 2 separate arms: primary prevention and secondary prevention (60 in each arm). In the primary prevention arm, 60 patients who have received CF-LVAD implantation and have not experienced any episodes of GI bleeding will be assigned to an O3FA group or a control group, with 30 patients in each group. In the secondary prevention arm, 60 LVAD patients who have experienced at least 1 episode of GI bleeding after CF-LVAD implantation will be assigned to an O3FA group or a control group, with 30 patients in each group. Randomization will be performed using computer software, and initiation of therapy will start within 24 hours of randomization. O3FA will be given at a dose of 4,000 mg orally per day, and all patients will receive guideline-directed medical therapy during the study period.

The following study procedures will be performed:

Baseline

Subject to sign consent
Verify inclusion/exclusion criteria
Record medical history and medications
Collect stool sample
Collect blood sample
Randomization
For O3FA subjects:
-Provide O3FA supplement
-Subjects will be instructed to take 4 pills a day

1.5 months post-randomization

Record medical history and medications
Record adverse events

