Statistical analysis will be performed using SPSS Statistics 22 (SPSS Inc, Chicago, IL, USA). Variables with 2-tailed p value <0.05 will be considered significant. Clinical parameters and outcomes including rates of GI bleeding, angiogenesis-related biomarkers, inflammatory markers, and microbiome data will be compared between the O3FA and control groups, both among the primary and secondary prevention arms using unpaired t-test or Mann-Whitney U test as appropriate. A necessary patient number for each group is calculated as 26 (total 104) by power analysis with 0.05 of α , 0.8 of effect size, 0.8 of $1-\beta$.

A master list maintaining patient names and code numbers will be stored in locked files. A password-protected computer located in the heart failure main office will contain a database for data collected in this study. Case report forms (CRF's) will be generated and filled out for each subject enrolled in this study.

There is a risk of loss of confidentiality. If a patient agrees to participate, and signs an informed consent, a signed copy of the consent will be given to them, a copy placed in their record and then the data will be abstracted into an electronic database. The database will be within the Department of Medicine, Section of Cardiology. The data will be password protected and covered by all of the firewalls and security features of the Department of Medicine.

The investigators seek to minimize these risks by labeling the study related data and specimens with a study code. This study code will be linked with the patient's data. Only the investigators

and their designated staff will have access to the databases and the link between study code numbers and patient identifying information.

Data and samples may be utilized by faculties who have the proper IRB approval to do so, and whose study objective meets with the overall objective of this research.

We may share coded data and/or samples outside of the institution in collaboration efforts. An IRB amendment will be submitted to the IRB for review if this happens. Additionally, if NIH funding is obtained for any proposed study, it is possible that the PI will be required to provide a copy of coded data to the NIH for public use. In either case, direct patient identifiers will never be shared.

ECONOMIC BURDEN TO PARTICIPANTS

There will be no economic burden to the participants.

CONSENT PROCESS

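### In the secondary-prevention arm, adjusting the GI-bleeding comparison for earlier bleeds and time since implant would add modest precision at almost no cost

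*Combined protocol and SAP*

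**What the plan says.** Under Procedures Involved, the secondary-prevention arm consists of "60 LVAD patients who have experienced at least 1 episode of GI bleeding after CF-LVAD implantation", split 30 to O3FA and 30 to control. The number of earlier bleeds has no upper limit. Under Objectives, Aim 1a sets a window of up to 3 months after implantation for patients without a bleed; Aim 1b sets no window for those with one. Randomisation is by computer software, with no stratification by bleed history beyond the split into the two arms.

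Under Statistical Analysis, Data Management, and Confidentiality, "outcomes including rates of GI bleeding, angiogenesis-related biomarkers, inflammatory markers, and microbiome data will be compared between the O3FA and control groups", within each prevention arm, "using unpaired t-test or Mann-Whitney U test as appropriate". No covariate, count model or follow-up offset is named.

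Study Endpoints makes the rate of GI bleeding a secondary endpoint, and Aim 3 asks for it in each population. The baseline visit records medical history, but neither the number of earlier bleeds nor the time since implant is a named data item.

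Background gives the retrospective pilot result for O3FA against control as "0.077 ± 0.419 events/year vs. 0.305 ± 0.847 events/year", with 1-year event-free rates of 97% and 79%.

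**The concern.** A patient with one bleed in two years of support and a patient with four bleeds in six months count alike in this arm. If bleeding tendency is partly a stable feature of the patient, the earlier count predicts the later one. An unadjusted comparison then leaves that predictable variation in the error term. With 30 against 30, repeat bleeders can also fall unevenly between the groups by chance, and part of the observed rate difference would then reflect case mix. Adjusting for a value fixed before randomisation recovers some of this without adding patients. The point does not arise in the primary-prevention arm, where every patient has zero earlier bleeds.

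**Working it through.** **1. The plan's own figure.** The plan states: "A necessary patient number for each group is calculated as 26 (total 104) by power analysis". With two-sided α 0.05, standardised effect 0.8 and power 0.8, the normal approximation gives 2(1.960 + 0.842)²/0.8² = 24.5, or 25 per group. The exact t calculation gives 25.5, rounded up to 26, and 4 × 26 = 104. Power is 80.7% at 26 and 86.1% at 30. The figure reproduces and is not in dispute. The endpoint it refers to is not named.

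**2. What the pilot suggests about uneven risk.** With equal risk, independent events and one year of follow-up each, counts would be Poisson.

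- Control variance: 0.847² = 0.717. Variance/mean: 0.717/0.305 = 2.35, against 1 for Poisson.
- Dispersion k, where variance = mean + k·mean²: (0.717 − 0.305)/0.305² = 4.43.
- Event-free at equal risk: exp(−0.305) = 73.7%, against 79% reported. Solving (1 + 0.305k)^(−1/k) = 0.79 gives k = 2.10.
- O3FA group: 0.419²/0.077 = 2.28, and exp(−0.077) = 92.6% against 97% reported.

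The two control values of k differ: k = 4.43 would predict 82.5% event-free, not 79%. They are therefore used as a range.

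**3. How much bleed history would explain.** The documents give no correlation between earlier and later bleeds, so this step rests on assumptions: gamma-Poisson counts, a stable rate per patient, source-population mean 0.305/year, entry with at least one bleed, and earlier support of 1 year or of 0.25-3 years. R² is the share of next-year count variance explained; the gain in patients is 1/(1 − R²) − 1.

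| k | Earlier support | R², count as 1, 2, 3+ plus months | Gain | R², full count used optimally with exposure | Gain |
|---|---|---|---|---|---|
| 2.1 | 1 year | 0.084 | 9% | 0.095 | 10% |
| 2.1 | 0.25-3 years | 0.104 | 12% | 0.139 | 16% |
| 4.4 | 1 year | 0.175 | 21% | 0.227 | 29% |
| 4.4 | 0.25-3 years | 0.181 | 22% | 0.293 | 41% |

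Log count alone, with 0.5 to 2 years of earlier support, correlates with the later count as follows:

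- k = 1.5: 0.175-0.300 (R² 0.03-0.09)
- k = 2.0: 0.222-0.356 (R² 0.05-0.13)
- k = 4.43: 0.366-0.519 (R² 0.13-0.27)

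**4. Power, 30 per group.** At an assumed rate ratio of 0.5, adjusting linearly for grouped count plus months (4,000 simulated trials per setting) moves power from 34.5% to 34.9% and from 32.7% to 33.1% at k = 2.1. At k = 4.4 it moves from 39.6% to 43.7% and from 35.4% to 40.0%. Allowing for variation between simulations, the rise is about 0-3 points at 2.1 and 4-5 at 4.4.

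At an assumed rate ratio of 0.4 (1,000 trials per setting), quasi-Poisson with log count has 43.9-48.2% power against 42.9-49.0% for the t-test at k = 1.5, which is no gain. At k = 4.43 it has 64.5-67.0% against 52.8-57.9%. Its rejection rate under no effect is 4.6-5.4%.

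**5. Chance imbalance.** A one-standard-deviation chance difference in mean earlier count shifts the unadjusted difference by ρ·SD·√(2/30)/mean, as a fraction of the control mean. For k = 2.0 and 1 year of earlier support this is 0.296 × 1.055 × 0.258/0.734 = 11%; for k = 4.43 it is 0.478 × 1.516 × 0.258/1.129 = 17%. Over k = 1.5 to 4.43 and 0.5 to 2 years the range is 7-21%. An imbalance in history-predicted rate as large as the whole pilot difference (0.305 − 0.077 = 0.228 events/year) occurs in 1-2.5% of trials at k = 2.1 and about 24% at k = 4.4.

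**6. What adjustment cannot do.** The pilot standardised effect is 0.228/√[(0.847² + 0.419²)/2] = 0.228/0.668 = 0.34. At 30 per group the t-test has about 26% power for it. With a correlation of 0.4 that becomes 29%, and with 0.5, 32%.

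**The case against.** The best case for leaving the plan alone is that the endpoint is secondary, the randomised comparison is valid as it stands, and the benefit is uncertain. Much of this stands.

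- **Bias.** A reader might infer that ignoring bleed history biases the result. It does not: randomisation makes the unadjusted difference unbiased on average, and its standard error already allows for chance imbalance.
- **Uneven risk.** A reader might take the pilot figures as proof of very uneven risk. Follow-up lengths in that cohort are not given, and short follow-up alone could produce variance/mean of 2.35. Clustered rebleeds could do the same without stable differences between patients. The gap of 79% against 74% is only 1.0-1.5 standard errors if the control group had 60-140 patients (its size is not stated; the whole cohort was 166). Nor is the cohort described as prior bleeders.
- **Stable rates.** Background cites registry rates falling from 16.24 to 4.08 events per 100 patient-months after month 3. Earlier counts therefore depend partly on how much early time a patient accrued. Months since implant addresses this only in part.
- **Size.** A reader might infer a gain of up to 41% more patients. That needs the upper dispersion value, varied earlier support and optimal use of the full count.
- **Availability.** A reader might assume the count is already in the database. Arm placement requires at least one bleed to be established and medical history is taken, but neither the count nor months since implant is a named item.

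None of this makes adjustment harmful. It places the benefit between about nil and moderate, against a very small cost.

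**Conclusion.** The point holds as an optional efficiency improvement. The plan makes no use of bleed history within the secondary-prevention arm, in allocation or in analysis. Under a stable gamma-Poisson rate with dispersion 2.1 to 4.4, grouped count plus months since implant explains about 8-18% of next-year variance, equal to about 9-22% more patients; the full count with exposure could reach about 9-29% of variance. The gain in power is near nil at the lower dispersion, moderate at the upper, and approaches zero if risk resets after a bleed. Adjustment does not rescue power for an effect of pilot size. The documents do not support calling the planned comparison biased or the uneven risk established. Prespecifying the covariates has one further merit: in an open-label trial it removes the option of choosing them after results by group have been seen.

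**What to change.** Add to the Statistical Analysis section, choosing one of the two models in advance: *In the secondary-prevention arm, the number of GI bleeds after randomisation will be analysed by a [negative binomial / quasi-Poisson] model with treatment group, log number of GI bleeds between implantation and randomisation, log months from implantation to randomisation, and log follow-up time as offset. The unadjusted comparison will also be reported.*

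A named model is needed because neither a t-test nor a Mann-Whitney test takes a covariate. The simulations above used quasi-Poisson and linear models; negative binomial was not simulated. Log count is preferable to three categories because it keeps more of the information and uses one degree of freedom.

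Record the bleed count since implantation and the implant date on the baseline case report form, from the medical history already taken.

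Cost: one addition to the analysis text, two form fields and two degrees of freedom. No patients, visits or procedures are added.

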PROTOCOL TITLE

Open-Label Prospective Randomized Control Trial to Investigate the Efficacy of Omega-3 Fatty Acid Therapy in Preventing Gastrointestinal Bleeding in Patients with Continuous-Flow Left Ventricular Assist Device

Version: 05Jun2019

NCT03784963

PROTOCOL TITLE

Open-Label Prospective Randomized Control Trial to Investigate the Efficacy of Omega-3 Fatty Acid Therapy in Preventing Gastrointestinal Bleeding in Patients with Continuous-Flow Left Ventricular Assist Device

PRINCIPAL INVESTIGATOR

[name]
Department of Medicine, Section of Cardiology
[contact]

OBJECTIVES

Aim 1: We will evaluate whether high-dose omega-3 fatty acid (O3FA) supplementation alters markers of angiogenesis and inflammation in patients with continuous-flow left ventricular assist devices (CF-LVAD).

- **Aim 1a** will assess the effect of high-dose O3FA in patients who have not experienced an episode of gastrointestinal (GI) bleeding. Patients will be enrolled up to 3 months following CF-LVAD implantation and randomized to high-dose O3FA or none. Markers of angiogenesis and inflammation will be assessed prior to and following initiation of high-dose O3FA therapy.
- **Aim 1b** will assess the effect of high-dose O3FA in CF-LVAD patients who have already experienced a GI bleeding event. Patients who have experienced a prior bleeding event will be enrolled and randomized to high-dose O3FA or none. Markers of angiogenesis and inflammation will be assessed prior to and following initiation of high-dose O3FA therapy.

Aim 2: We will assess the changes that occur to the microbiome of CF-LVAD patients following O3FA supplementation.

Aim 3: We will assess the effect of high-dose O3FA supplementation on GI bleeding events in both the population without prior GI bleeding events, and the population with prior GI bleeding events.

BACKGROUND

Continuous-flow left ventricular assist devices (CF-LVAD) have become the mainstay of therapy for advanced heart failure, both as bridge to transplantation and as destination therapy, allowing significant improvement in survival. However, this therapy is limited by a high adverse event profile, specifically those related to hemocompatibility.

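### Primary-prevention bleeding comparison: randomisation and analysis ignore time since implant and baseline ACEI/ARB use, leaving a modest, cheaply avoidable conditional bias in a secondary endpoint

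*Combined protocol and SAP*

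**What the plan says.** - **Allocation (Procedures Involved).** "Randomization will be performed using computer software, and initiation of therapy will start within 24 hours of randomization". Each prevention arm has 60 patients, 30 per group. No stratification factor other than prior bleeding, which defines the arms, is named.
- **Entry window (Objectives, Aim 1a).** For patients without a prior bleed: "Patients will be enrolled up to 3 months following CF-LVAD implantation and randomized to high-dose O3FA or none". Aim 1b, for patients with a prior bleed, sets no window.
- **Bleeding rates (Background).** The registry figure for the early period is "16.24 events of GI bleeding per 100 patient months in the first 3 months after implantation". For months 3 to 12 the rate on the same scale is given as 4.08.
- **ACEI/ARB (Background).** Of patients without angiotensin II antagonism 48% bled, whereas "only 24% of the patients who received ACEI or ARB experienced GI bleeding".
- **Analysis (Statistical Analysis).** Bleeding rates, biomarkers and microbiome data are compared between groups within each arm "using unpaired t-test or Mann-Whitney U test as appropriate". No covariate is mentioned.
- **Status of GIB (Study Endpoints).** GIB rate is a secondary endpoint; the primary endpoint is change in angiogenesis markers. GIB is also the subject of Aim 3 and appears in the trial title.

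**The concern.** A patient randomised in the first week after implant spends most of the high-risk period inside the study year. One randomised in week 12 has almost none of it left. Both are eligible for the primary arm, and nothing in the allocation or the analysis accounts for the difference. The same applies in both arms to ACEI/ARB use, which the Background associates with halved bleeding.

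With 30 patients per group, visible chance imbalances in such factors are not rare. If one occurs, the unadjusted GIB comparison is tilted by a known cause. Any correction would then be chosen after the data had been seen, which makes the Aim 3 result harder to interpret.

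**Working it through.** **Inputs from the protocol.** GIB rates of 0.1624 per patient-month in months 0–3 and 0.0408 in months 3–12; entry at month t, 0 ≤ t ≤ 3; 12 months of follow-up; 30 per group; bleeding 48% v 24% by ACEI/ARB; the investigators' retrospective rates of 0.077 v 0.305 events/year (control SD 0.847).

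**Assumptions not in the protocol.** The registry rates apply to these patients; 0.0408 continues just past month 12; entry times are either uniform over 0–3 months or, as an extreme, half at day 0 and half at month 3; 30–70% of patients use ACEI/ARB.

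**1. Spread in expected events.** The rate ratio is 16.24/4.08 = 3.98. Expected study-year events are 0.1624 × (3 − t) + 0.0408 × (9 + t):

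| Entry month | 0 | 1 | 2 | 3 |
|---|---|---|---|---|
| Events per patient | 0.854 | 0.733 | 0.611 | 0.490 |

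The fourfold rate ratio therefore shrinks to 0.854/0.490 = 1.75-fold over a full year. The mid-window mean is 0.672.

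**2. Share of variance due to time since implant.** The slope is 0.1624 − 0.0408 = 0.1216 events per month.
- Uniform entry (variance of t 0.75): 0.1216² × 0.75 = 0.0111; share 0.0111/(0.0111 + 0.672) = 1.6%.
- Half/half entry (variance 2.25): 0.0333/(0.0333 + 0.672) = 4.7%.

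These shares assume Poisson counts; overdispersion makes them smaller.

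**3. A 20-point imbalance (18 v 12 early entrants), half/half case.**
- Probability of this or worse, hypergeometric with 60 patients and 30 early: 0.196.
- Shift: 0.20 × (0.854 − 0.490) = 0.073 events per patient, or 0.073/0.672 = 11% of the mean and 0.073/0.228 = 32% of the retrospective difference (0.305 − 0.077).
- Poisson SE of the group difference: √(2 × 0.672/30) = 0.212. The shift is 0.073/0.212 = 0.34 SE.
- Conditional two-sided error by normal approximation: P(Z > 1.96 − 0.34) + P(Z < −1.96 − 0.34) ≈ 6.4%.

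Under uniform entry, a 95%-extreme imbalance in mean entry time is 1.96 × √0.75 × √(2/30) = 0.44 months, which shifts the difference by 0.44 × 0.1216 = 0.053 events.

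**4. The same at the investigators' own control rate.** An 11% shift on 0.305 is 0.033 events. The SE is 0.847 × √(2/30) = 0.219, so the shift is 0.15 SE.

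**5. ACEI/ARB.** With a proportion p using it, the share of variance in bleeding (yes/no) is p(1 − p) × 0.24² / [q(1 − q)], where q = 0.48 − 0.24p. This gives 5.0% (p = 0.3), 6.3% (p = 0.5) and 5.6% (p = 0.7). A 20-point imbalance shifts incidence by 0.20 × 24 = 4.8 points. At p = 0.5 the SE is √(2 × 0.36 × 0.64/30) = 12.4 points, so this is 0.39 SE.

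**6. Operating characteristics.** These come from simulation: 40,000 trials per scenario, 30 v 30, Poisson counts with and without gamma frailty of variance 1, comparing a t-test with linear adjustment for entry time. Ranges cover both entry patterns unless stated.

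| Quantity | Unadjusted | Adjusted |
|---|---|---|
| Type I error | 0.047–0.051 | 0.047–0.051 |
| Power, rate ratio 0.5 | 0.28–0.44 | 0.28–0.43 |
| Power, rate ratio 0.25 | 0.69–0.87 | 0.69–0.87 |
| Type I error in worst 5% of imbalances, half/half entry | 0.062–0.081 | 0.044–0.056 |

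The simulation modelled entry time only, and used linear adjustment rather than a count model.

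**The case against.** The strongest reply is that randomisation already deals with chance imbalance. A reader might infer from the fourfold fall in rates that the design lets imbalance mimic or hide an O3FA effect. The figures do not support that: overall type I error is near 5% without adjustment, average power barely changes, and a fairly unlucky imbalance moves the estimate by about a third of an SE. This part of the objection stands.

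Four further limits also stand.
- **Only one arm has the 0–3 month window.** The registry rates do not describe patients who have already bled. A reader might extend the argument to time since last bleed in the secondary arm, where entry is unrestricted, but the protocol gives no rates by that interval.
- **The extreme entry mix is assumed.** Uniform entry, or the investigators' lower control rate, makes the shift smaller.
- **The ACEI/ARB contrast compares treated with untreated patients.** The 4.8-point shift reads it as fully causal. The protocol gives no prevalence of use, and guideline-directed therapy for all patients may narrow differences in use.
- **The rates concern bleeding only.** They give no size for any effect on the primary biomarker endpoint. The Background does link angiotensin II to Ang-2, but without figures for this population.

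What the objection does not remove is the conditional argument. The trial is run once, the factors are identified in its own Background, and a covariate named in advance avoids a post hoc choice.

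**Conclusion.** Upheld as a minor point. Within the primary-prevention arm, neither allocation nor analysis accounts for time since implant, which by the protocol's rates gives up to a 1.75-fold range in expected study-year bleeding. In both arms the analysis ignores baseline ACEI/ARB use. The consequence is modest conditional bias in a secondary endpoint: for a 20-point imbalance in early entry, about 0.07 events per patient (0.34 SE) at registry rates and about 0.03 (0.15 SE) at the investigators' own control rate. The precision lost is small: about 2–5% of GIB variance for time since implant and 5–6% for ACEI/ARB. These sizes rest on the assumptions listed with the calculation. The validity of the test is not in question.

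**What to change.** 1. **Randomisation, primary arm.** Stratify by time since implant in two levels, for example split at the midpoint of the 3-month window. Expected events fall linearly across the window, so a midpoint split is natural; under uniform entry it removes three quarters of the variance in entry time (within-stratum variance 1.5²/12 = 0.1875 against 0.75).
2. **GIB analysis, primary arm.** Replace the t-test or Mann-Whitney U test with a prespecified count-regression model, for example negative binomial with log follow-up time as offset, including treatment, time since implant and baseline ACEI/ARB use.
3. **GIB analysis, secondary arm.** Use the same model with treatment and baseline ACEI/ARB use. Time since last bleed is optional, because the documents give no rates to support it.

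**Cost.** One extra stratum in the primary arm, a model in place of a simple test, and the implant date recorded explicitly at baseline. The baseline visit lists only medical history and medications, but the adopted bleeding definition already depends on days since implant, so the date is needed anyway. Medications are already recorded. No extra patients, visits or tests are required.
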